#### SPONSOR: GW PHARMA LIMITED

# 12.4 Pregnancy

Any patient, or patient's partner, who becomes pregnant while receiving the IMP, or within 3 months of the last dose of IMP, must be reported to the GW PVD using the GW Pregnancy Monitoring forms provided. Where possible, the investigator should provide the outcome of the pregnancy.

All pregnancies must be recorded in the eCRF within 24 hours of becoming aware. The GW PVD will be automatically notified that a pregnancy has been recorded. Any additional information required for a case (follow-up or corrections to the original case) will be requested by GW PVD through eCRF queries where data is entered in EDC.

The investigator is not obliged to actively monitor for any pregnancies that commence more than 3 months after the final dose of IMP. However, if the investigator becomes aware of a new pregnancy outside this time limit, then he/she should report it as above. The GW PVD will follow up for all pregnancy outcomes.

#### 12.5 Causality Assessment

Causality assessment is required for all AEs and SAEs. Causality assessment must only be assigned by the investigator. All cases judged as having a reasonable suspected causal relationship to the IMP must be reported as such. The expression *"reasonable causal relationship"* is meant to convey in general that there are facts (evidence) or arguments to suggest a causal relationship.

The following question, which must be answered by the investigator for all AEs, is used to capture the reasonable causal relationship of an event to the IMP:

"In your opinion is there a plausible relationship to the IMP?" The answer is either "yes" or "no."

Events that start before the first dose of IMP (pretreatment) should be considered as not causally related. Where a pre-treatment event worsens in severity following the first dose of IMP, a new event record should be entered into the eCRF.

Considering the explanation given above, investigators are strongly encouraged to express their opinion on what the cause of an AE might be. For individual patients, the investigator is usually in the best position to assess the underlying suspected cause of an AE. For all AEs and especially SAEs, it is important that the investigator assess not only the possible role of the IMP but also other potential contributing factors. Factors for consideration of the underlying cause may include the following:

- Medical and disease history
- Lack of efficacy/worsening of treated condition
- Concomitant or previous treatment
- Withdrawal of IMP
- Protocol-related procedure

#### 12.6 Reporting Procedures for All Adverse Events

All AEs (including SAEs) occurring during the trial will be reported on the running logs in the AE section of the eCRF. This includes all events from the time following Screening (Visit 1) up to and including the Safety Follow-up Visit (Visit 7), whether or not attributed to the IMP and observed by the investigator or patient.

The following information will need to be provided for all AEs:

#### A) Adverse Event (Diagnosis or Syndrome if Known or Signs and Symptoms)

Where the investigator cannot determine a diagnosis, signs or symptoms should be recorded in the AE section of the eCRF. Once a diagnosis has been determined, the AE section of the eCRF must be updated to reflect the diagnosis in replacement of the original symptoms. In circumstances where only a provisional diagnosis is possible (working diagnosis), the eCRF must be updated to reflect the provisional diagnosis in replacement of the original symptoms. In some circumstances, it may be relevant for the investigator to include the symptoms alongside the diagnosis in the verbatim event description. However, the diagnosis (full or provisional) should be clearly stated, e.g., symptom due to disease (i.e., weakness due to cancer, tremor due to MS, headache and fever due to pneumonia, and generalized weakness due to hepatic cancer progression).

#### B) Adverse Event Start Date and Stop Date

The start and stop dates of the event must be provided. All AEs require these fields to be completed in full. Partial dates or missing dates are not normally acceptable, and significant effort must be undertaken to obtain any unknown information. If a precise date is not known, an estimated date should be provided instead. When a complete date cannot be given, as much information as possible (i.e., month and year or, in exceptional circumstances, just year) should be recorded. When the actual start date becomes known, the eCRF must be updated to replace the previously recorded date.

#### SPONSOR: GW PHARMA LIMITED

#### C) Outcome

The outcome of the event must be recorded accurately and classified into 1 of the following categories:

- Recovered/Resolved
- Recovered/Resolved with sequelae
- Not Recovered/Not Resolved
- Fatal

#### D) Severity

When describing the severity of an AE, the terms mild, moderate, or severe should be used. Clinical judgment should be used when determining which severity applies to any AE.

If the severity of an AE fluctuates day-to-day, e.g., a headache or constipation, the change in severity should not be recorded each time; instead, only the worst observed severity should be recorded with AE start and stop dates relating to the overall event duration, regardless of severity.

A severe AE is not the same as an SAE. For example, a patient may have severe vomiting, but the event does not result in any of the SAE criteria above. Therefore, it should not be classified as serious.

#### E) Causality

See Section 12.5 above.

#### F) Action Taken with Trial Medication

This question refers to the action taken with the IMP due to an AE. The action with the IMP must be classified as follows:

- Dose Not Changed
- Dose Reduced
- Drug Interrupted
- Drug Withdrawn

#### 12.7 Follow-up Procedures for Adverse Events

The investigator may be asked to provide follow-up information to the GW PVD for any AEs reported or during the investigation of potential safety issues. Such requests for additional safety information may occur after Visit 7, after the trial.

AEs considered related to the IMP by the investigator or the sponsor should be followed up until resolution or the event is considered stable.

It will be left to the investigator's clinical judgment whether or not an AE is of sufficient severity to require the patient's discontinuation of treatment. A patient may also voluntarily withdraw from treatment due to what he or she perceives as an intolerable AE. Further details of withdrawal are presented in Section 10. If either of these occurs, the patient must undergo an end of treatment assessment and be given appropriate care under medical supervision until symptoms cease or the condition becomes stable. If a safety concern is identified following withdrawal of a patient, GW may contact the investigator for additional follow-up information.

# 12.8 Potential Cases of Drug-induced Liver Injury

All trial sites are required to submit to the GW PVD the laboratory results for any patient after randomization who meets the criteria for the following selected laboratory parameters:

- ALT or AST  $> 3 \times$  ULN with the appearance of fatigue, nausea, vomiting, right upper quadrant pain or tenderness, fever, rash, and/or eosinophilia (> 5%)
- ALT or AST  $> 8 \times ULN$
- ALT or  $AST > 5 \times ULN$  for more than 2 weeks
- ALT or AST  $> 3 \times$  ULN and (TBL  $> 2 \times$  ULN or INR > 1.5)

These reports must be sent to the GW PVD via email within 24 hours of becoming aware of the results (see APPENDIX 2 for GW PVD contact details). In addition, a copy of the patient's baseline laboratory results together with all reports to the GW PVD. Any laboratory results that constitute an AE in the investigator's opinion must be recorded in the eCRF. Where the results are considered to be SAEs, these must be recorded in the eCRF within 24 hours of becoming aware of the result, in line with reporting procedures for SAEs (Section 12.3).

Abnormal values in AST and/or ALT concurrent with abnormal elevations in TBL that meet the criteria outlined above are considered potential cases of drug-induced liver injury and will be considered as protocol-defined criteria for IMP discontinuation and important medical events. The investigator will arrange for the patient to return to the trial site as soon as possible (within 24 hours of notice of abnormal results) for repeat assessment of ALT, AST, TBL, alkaline phosphatase, gamma-glutamyl transferase, INR, and hematology parameter levels; detailed history; and physical examination. Patients should be followed in this way until all abnormalities have normalized (in the investigator's opinion) or returned to the baseline state.

Elevations in ALT or AST >  $3 \times$  ULN or TBL >  $2 \times$  ULN alone are not considered potential cases of drug-induced liver injury, but will be followed as detailed above, within 72 hours' notice of abnormal results. If the patient cannot return to the trial site, repeat assessments may be done at a local laboratory and the results sent to GW PVD.

#### 12.9 Notification of Safety Information to Investigators, Regulatory Authorities, and Institutional Review Boards/Independent Ethics Committees

In accordance with the EU Clinical Trials Directive, relevant parts of the FDA Code of Federal Regulations, and any national regulations, GW will inform investigators, regulatory authorities, and relevant IRBs/IECs of all relevant safety information. This will include the reporting of relevant SAEs and all suspected unexpected serious adverse reactions (SUSARs).

This information will be provided through 3 sources:

- 1) IB: This document is a compilation of the clinical and non-clinical safety data available on the IMP that are relevant to the trial. The IB is updated annually.
- Development core safety information: this document forms the safety section of the IB or is updated as an addendum to the IB. This document is revised, if necessary, when new important safety information becomes available.
- 3) Council for International Organizations of Medical Sciences (CIOMS) reports: these reports are issued every time a SUSAR is reported to GW. They provide information on individual case reports and are sent to all the regulatory authorities, the relevant central ethics committees that have approved the trial, and the investigators. As required, the investigator should notify their regional IRBs/IECs of SAEs or SUSARs occurring at their trial site and other AE reports, i.e., CIOMS reports and any additional safety documentation received from GW, in accordance with local procedures.

In the US, investigators are normally required to report promptly to their IRBs all unanticipated problems involving risks to patients, or others, including AEs that should be considered unanticipated problems. Based on current FDA guidance, the following clarification is provided in determining what constitutes an unanticipated problem:

In general, an AE observed during the conduct of a trial should be considered an unanticipated problem involving risk to patients and reported to the IRB, *only* if it were unexpected, serious, and would have implications for the conduct of the trial (e.g., requiring a significant, and usually safety-related, change in the protocol such as revising inclusion/exclusion criteria or including a new monitoring requirement, informed consent, or IB). An individual AE occurrence *ordinarily* does not meet these criteria because, as an isolated event, its implications for the trial cannot be understood.

The FDA guidance states that, accordingly, to satisfy the investigator's obligation to notify the IRB of unanticipated problems, any investigators participating in a multicenter trial may rely on the sponsor's assessment and provide to the IRB a report of the unanticipated problem prepared by the sponsor.

GW will inform investigators, regulatory authorities, and relevant IRBs/IECs of any safety issues or case reports that are considered to be unanticipated and provide such reports as mentioned above. It should be noted that a single SUSAR report notified to investigators in the trial does not necessarily constitute an unanticipated problem unless identified by GW in the submission cover letter.

As a minimum, the recipient will be sent all of the above and relevant updates between the period from ethical approval and final database lock.

#### SPONSOR: GW PHARMA LIMITED

# **13 STATISTICAL CONSIDERATIONS**

Further details of the proposed statistical analysis will be documented in a statistical analysis plan (SAP), which will be produced prior to unblinding of the trial. Any deviations from the original SAP will be described in the final clinical study report.

# 13.1 Sample Size, Power, and Significance Levels

446 patients will be randomized to the nabiximols or placebo treatment arms on a 1:1 basis.

The following assumptions have been used for the sample size:

- Common standard deviation of 6.5 for the change from baseline in average daily spasm count for nabiximols and placebo treatment arms
- True mean difference of -2 between the mean change from baseline in average daily spasm count in the nabiximols treatment arm compared to the placebo treatment arm

Using the above assumptions, the total sample size of 446 patients (223 patients per treatment arm) will have 90% power to detect a difference between treatment arms in change from baseline in average spasm count of -2 using a 2-sided hypothesis test at the 5% significance level.

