# 7.2 Randomization

The allocation of IMP to treatment number will be done according to a randomization schedule produced by an independent statistician. The treatment allocation schedule will have balanced randomly permuted blocks, stratified by region (US versus non-US) and prior cannabis use defined as any pattern of recreational or medicinal use, which would typically exclude isolated, unintentional, or passive exposures. Investigator judgment should be applied during the clinical interview to determine if there is a history of intentional, repeated use of cannabis or cannabinoid products. The randomization schedule will be held centrally on the IRT and not divulged to any other person involved in the trial until the database has been locked and unblinding authorized by the relevant GW personnel. For access to blinded treatment assignment, see Section 8.5. Patients who withdraw from the trial will not be replaced.

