# 13.6.1 Primary Endpoint

The primary endpoint is the change from baseline in average daily spasm count (the average daily spasm count from Days 57 to 84 compared to the average daily spasm count for the baseline period) for all randomized patients regardless of treatment compliance.

The average daily spasm count will be calculated for the baseline period and each 28-day period corresponding to Days 1 to 28, Days 29 to 56, and Days 57 to 84. The change from baseline for average daily spasm count will be calculated for Days 1 to 28, Days 29 to 56, and Days 57 to 84.

Average daily spasm count for each period is defined as follows:

Total spasm count for the period Number of days in which the daily diary was completed during the period

For post-randomization data, the average daily spasm count over the 28-day period will only be calculated if there are  $\geq 15$  days of non-missing data and < 10 consecutive days of missing data. If there are < 15 days of non-missing data or  $\geq 10$  consecutive days of missing data then the average daily spasm count for the 28-day period will be set to missing.

The average daily spasm count and change from baseline will be summarized by treatment for each 28-day period.

The change from baseline will be analyzed using mixed model repeated measures (MMRM), using data for each 28-day period. The model will include baseline average daily spasm count, prior cannabis use, region (US versus non-US), period, treatment arm,

period by treatment arm interaction, and period by baseline interaction as fixed effects. Period repeated within each patient will be included as a repeated effect. Denominator degrees of freedom adjustment will be performed using the Kenward-Roger method.

The within-patient correlation structure will be modelled using an unstructured covariance matrix. If the model does not converge the following structures will be used in order of preference Toeplitz, first-order autoregressive and Compound symmetry.

The least squares mean estimates for each treatment arm and period, along with the standard error and 95% confidence intervals (CIs), will be presented. In addition, estimates of the treatment difference at each period in change from baseline will be presented along with standard errors of the difference and 95% CIs. The primary comparison is the estimate of the treatment difference for the Days 57 to 84 period.

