8.2 Sample Size Considerations

A total of 446 patients are planned to be randomized to the nabiximols or placebo treatment arms on a 1:1 basis.

The following assumptions have been used for the sample size:

- Common standard deviation of 6.5 for the change from baseline in average daily spasm count for nabiximols and placebo treatment arms
- True mean difference of −2 between the mean change from baseline in average daily spasm count in the nabiximols treatment arm compared to the placebo treatment arm

Using the above assumptions, the total sample size of 446 patients (223 patients per treatment arm) will have 90% power to detect a difference between treatment arms in change from baseline in average spasm count of -2 using a 2-sided hypothesis test at the 5% significance level.

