5.0 Scope

This addendum supplements the SAP.

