6.0 Introduction

This SAP addendum should be read in conjunction with the study protocol V5.0 01JUN2021, CRF V3.0 05NOV2021 and SAP V1.0 22MAR2022.

Final approval of the SAP addendum will occur prior to study unblinding.

The decision was made on 9th November 2022 to discontinue the study and halt any further enrollment of patients without the planned number of patients being recruited. As a result of this, an abbreviation of the planned analysis and reporting as detailed in the protocol and SAP will be carried out. The possibility of early termination was described in Protocol Section 16.1.

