7.0 Statistical Methods

The abbreviated reporting will follow the strategy as detailed in **Table 7-1**. Although the study will terminate early, the primary hypothesis will still be tested as per the final SAP.

Addendum to Statistical Analysis Plan for Protocol GWSP18023 (17-FEB-2023)

Table 7-1 Strategy for abbreviated reporting

Hierarchy	Strategy	Endpoint	Relevant Sections of SAP V1.0 to be Used
Primary & C Secondary Efficacy s Endpoints ((n	Conduct primary inferential analysis, standard descriptive statistics and listing. Sensitivity and supplemental (including subgroup analyses) will not be conducted. Figures will not be produced.	Daily spasm count	12.5.2.1 & 12.5.2.4
		MSSS-88	12.5.3.1 & 12.5.3.4
Secondary Safety Endpoints (excluding PK)	As described in SAP with the exception of figures, subgroup summaries, repeats on FAS.and those specific to an endpoint (detailed in final column).	TEAEs Clinical laboratory tests	 12.8.1 & 12.8.2 Excluding the following summaries: by time of first onset by AE duration of TEAEs related to IMP by maximum severity of TEAEs related to IMP and leading to IMP discontinuation by maximum severity of serious TEAEs related to IMP 12.8.3 Excluding the following summaries: Values outside of normal ranges Shift tables based on CTCAE v5.0 grade Shift tables based on normal range indicator will be presented by visit rather than by most extreme value and last
		Vital signs	on-treatment value.
		FCG	12.0.7
		C-SSRS	12.8.5.3
Secondary Safety Endpoints (PK)	No processing, analyses or reporting	PK	NA

Addendum to Statistical Analysis Plan for Protocol GWSP18023 (17-FEB-2023)

Exploratory	Listings only, no descriptive or	MSSS-88 subscales	12.5.3.4
Endpoints	inferential statistics or figures.	NRS spasm severity	12.5.4.2
		NRS spasticity	12.5.4.3
		T25FW	12.5.4.4
		SF-36	12.6.1
Other data	As described in SAP with the	Disposition	12.1
e s tł	exception of figures, subgroup summaries, repeats on FAS and those specific to a section (detailed in final column).	Demographics	12.2.1
		Disease Characteristics	12.2.5
		Medical History	12.2.4
		Prior and Concomitant	12.3.2
		Medications and	Excluding summaries of post-treatment medications
		Therapy	
		Treatment Exposure	12.3.1
		Protocol deviations	12.4
			Excluding summaries of major IPDs
		Other Safety	12.8.5.1, 12.8.5.4, 12.8.5.5, 12.8.5.6, 12.8.5.7
		Monitoring of Drug	12.8.6
		Abuse Liability	Excluding the summary of triggered events
	1		

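### Does the 90% power figure need to be restated now that enrollment stopped short of 446?

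*Protocol*

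**What the plan says.** Protocol 13.1 (Sample Size, Power, and Significance Levels) assumes a common SD of 6.5 for the change in average daily spasm count and a true difference of -2. On those assumptions, at two-sided 5%, "the total sample size of 446 patients (223 patients per treatment arm) will have 90% power to detect a difference between treatment arms". SAP 8.2 gives the same calculation and words the number as a plan: "A total of 446 patients are planned to be randomized to the nabiximols or placebo treatment arms on a 1:1 basis". No other power figure appears in either document, and neither section mentions an allowance for missing data.

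Two rules can reduce the number with a Days 57-84 value. Protocol 7.2: "Patients who withdraw from the trial will not be replaced". Protocol 13.6.1, where a period has too few diary days or too long a gap: "then the average daily spasm count for the 28-day period will be set to missing". SAP 10.17 has a similar rule but joins the two conditions with 'and' where the Protocol has 'or', so it would set fewer periods to missing.

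The SAP addendum records the decision to "halt any further enrollment of patients without the planned number of patients being recruited" (6.0 Introduction). On the primary analysis it says: "Although the study will terminate early, the primary hypothesis will still be tested as per the final SAP" (7.0 Statistical Methods). On its own standing it says: "This addendum supplements the SAP" (5.0 Scope) and "Final approval of the SAP addendum will occur prior to study unblinding" (6.0 Introduction). It gives no number randomized, no revised power and no expected interval width.

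**The concern.** There are two reasons for unease. First, 446 is exactly the uninflated two-sample requirement. Any missing Days 57-84 value takes an unadjusted comparison below 90%, withdrawals are not replaced, and sparse diary periods drop out.

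Second, and more seriously, the trial being analyzed is smaller than the one that was powered. Because the addendum adds to the SAP and does not replace it, SAP 8.2 still stands with its 90%. Someone looking at a non-significant result could turn to that section, find 90% power for -2, and take the result as good evidence against an effect of that size. If the evaluable total were around 200 or lower, that reading would be badly wrong. The addendum also drops the sensitivity and supplemental analyses, so the primary test carries more of the interpretation.

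**Working it through.** **Inputs.** From Protocol 13.1 and SAP 8.2: difference 2, SD 6.5, two-sided alpha 0.05, 223 per arm. Assumed, because the documents do not give them: the missing-data rate, the achieved evaluable total (equal arms) and the share of variance explained by covariates.

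**The plan's figure.** Normal approximation: n per arm = 2 × 6.5² × (1.960 + 1.282)² / 2² = 221.97, so 222 per arm. With the t distribution the standard error at 223 per arm is 6.5 × √(2/223) = 0.616 and the noncentrality is 2/0.616 = 3.25. Power is 90.01%; at 222 per arm it is 89.88%. The stated 446 and 90% therefore reproduce exactly, with no inflation.

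**Missing data in the trial as planned.** The planned test is not an unadjusted t-test. SAP 12.5.2.1 specifies a baseline-adjusted MMRM over three periods, and the estimand in Protocol Table 2-1 keeps data collected after treatment discontinuation. The plan does not say whether 6.5 is a raw or an adjusted SD. If it is raw and covariates explain 20% of the variance, the residual SD is 6.5 × √0.8 = 5.81.

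| Assumed missing | n per arm | Power, SD 6.5 | Power, SD 5.81 |
|---|---|---|---|
| 5% | 211 | 88.4% | 94.1% |
| 10% | 200 | 86.6% | 92.9% |
| 15% | 189 | 84.7% | 91.6% |
| 20% | 178 | 82.5% | 89.9% |

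Unadjusted, the loss is 2 to 8 points. With a modest covariate gain there is essentially none. A power deficit in the planned design is therefore not established.

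**The early stop.** The 95% CI half-width is t(0.975, N-2) × SD × √(2/(N/2)).

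| Assumed evaluable N | Power, SD 6.5 | Half-width | Power, SD 5.81 | Half-width |
|---|---|---|---|---|
| 446 (planned) | 90.0% | 1.21 | 95.2% | 1.08 |
| 400 | 86.6% | 1.28 | 92.9% | 1.14 |
| 300 | 75.7% | 1.48 | 84.4% | 1.32 |
| 200 | 58.1% | 1.81 | 67.8% | 1.62 |
| 100 | 33.1% | 2.58 | 39.9% | 2.31 |

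The evaluable totals needed for 90, 80 and 50% power are 446, 334 and 166 with SD 6.5, and 358, 268 and 132 with SD 5.81. A stop near the target costs little: 430 evaluable gives 88.9% and a half-width of 1.23.

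**What will be reported anyway.** Table 7-1 of the addendum keeps SAP 12.1 (numbers randomized and in each analysis set), 12.5.2.1 (least squares means, treatment difference, standard errors and 95% CIs) and 12.5.2.4 (summaries by 28-day period, which under SAP 12.0 include the non-missing n). These convey the loss of precision directly. With an observed difference of zero and SD 6.5, the interval at 200 evaluable would be about -1.81 to 1.81 and would exclude -2. At 100 it would be about -2.58 to 2.58 and would not. The interval tells the reader whether -2 is ruled out; the planned power does not.

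**The case for a change.** The best argument for acting is that a statement fixed while blinded cannot be suspected of having been shaped by the result, whereas the study report is written after unblinding. The addendum was still open to a sentence at that stage, blinded pooled counts would have sufficed, and the cost is one paragraph. Over a plausible range of achieved totals the fall in power is large.

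Part of this stands. The addendum would be more informative with the achieved number and an expected interval width, and no reader should carry the 90% over to the shortened trial. But the timing argument is weak here. Power recomputed at SD 6.5 and -2 depends only on the evaluable count, so it comes to the same figure before or after unblinding, and anyone with the reported n can work it out. Nor are readers left uninformed: a document due for approval before unblinding, and to be read together with the protocol and SAP, says that the planned number was not recruited. A single restated power could also mislead in its own way. At 300 evaluable, the unadjusted figure is 75.7% against 84.4% if covariates explain 20% of the variance, a gap of 8.7 points that the documents cannot resolve.

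**Conclusion.** No change to the plan is needed. Protocol 13.1 and SAP 8.2 make a conditional statement about 446 patients, it is correctly computed, and it remains true as a description of the design. It does not describe the shortened trial, and the addendum supplies the fact that tells the reader so.

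The omission is one of reporting. Following the documents as they stand still gives a valid primary test with its n, standard error and 95% CI. Restating power would change no estimand, population, test or decision rule, and a non-significant result would be read from the interval either way.

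The possible loss of power runs from about 1 point (430 evaluable, 88.9%) to 57 points (100 evaluable, 33.1%). Both totals are assumptions, with equal arms, SD 6.5 and no covariate gain; the real figure cannot be derived because the achieved number is not given. If the sponsor wishes, the study report could note that the 90% belonged to the planned 446, but nothing in the analysis depends on it.
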